8. **If we have permission to discuss study participation with Therapist/Clinic**, let the Therapist and/or clinic know the patient is enrolled in the study and ready to start their study therapy sessions and request they let us know when the client's first session will be (call and email; do not include patient name in email). **If we do not have permission to discuss study participation with Therapist/Clinic**, ask patient to let their therapist/clinic know they are ready to start their study therapy sessions and request they let us know when their first session will be.
9. **Send patient copy of their consent form and HIPAA auth**
 - a. In SurveyMonkey copy everything under "Collect" until the end of the consent form section and paste it to the end of the Consent Form template
 - b. In SurveyMonkey copy what's under "Collect" (through time spent) and the HIPAA section and paste to the end of the HIPAA authorization template
 - c. Save both as PDFs with following naming conventions:
Lastname,FirstInitial.FullRCT.PatientConsentForm
Lastname,FirstInitial.FullRCT.PatientHIPAA

(Use full first name if last name is same as someone else's)

Step 5: Collect dates from Therapist

NOTE: check Clinic details in [Participant Tracking DB](#). Some clinics will have already completed this session prior to informing client of study. In which case the below is irrelevant because it should already have been done before this point.

1. Record the client's care start date in the Tracking DB under the patient and therapist tabs
2. Record when the client's first session with their research therapist will be (the "Welcome/Get to Know You" Session).
3. Contact therapist after the Welcome/Get to Know You Session
 - a. Did the client attend this session?
 - b. Is the client eligible / appropriate for the study?
 - c. When is the first Study Therapy Session?
4. Record information in [Participant Tracking DB](#)
5. If eligible, continue to Step 6

WILLOW Full RCT Patient Protocol

6. If ineligible, discontinue client's participation
 - a. Log that the patient is ineligible in the tracking database and move cover sheet to the "Ineligible" folder.

Step 6: Scheduling Call

1. Make scheduling call as soon as you can, script below
2. If the patient doesn't answer the call, send scheduling email and leave the voicemail below.
3. Call back/email every 2 days until you reach patient.

Voicemail Script:

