If not, schedule a time to call back later. [Log the call in the tracking sheet, update the date of the call in both tracking sheet and database, and enter this new date into the calendar]

In this study, we're comparing how clients respond to different ways of delivering treatment for depression. As you know, you have been randomly assigned to the **[Standard Care or WILLOW]** condition.

We'll ask that you meet weekly with two or more study patients for 12 weeks each. We expect that you will first conduct a welcome/intake/get to know you session with the study patient to introduce the study to them and gauge if they would be a good fit. This does not count toward the 12 weeks. While the clients have gone through our screening process, we ask that you use your clinical judgment during this session to assess if the client is appropriate for the study or not. If your client is experiencing active mania or psychosis, meets criteria for alcohol or other drug abuse/dependence, is at imminent risk of suicide, or reports the occurrence of self-harm or self-injury in the past 30 days they should not be participating in this study. If you find your client meets any of the exclusion criteria, please let study staff know right away. We will work with you to discontinue the patient's participation in the study. It is up to you and your clinic if you decide to continue seeing the client outside of the study or if they should be assigned to another clinician. We will contact you after this initial session to verify that your client meets study criteria and will also at that time schedule your study assessments.

If assigned to Standard Care:

During your participation in this study, your clinic will assign you new study patients with depression. We ask that you treat them for depression as you would normally for 12 weeks. The patients will all be consenting study participants. They will complete study assessments at the same time points as you and will also receive payment for their participation. <<For Navos

WILLOW Full RCT Therapist Protocol

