### **Task 1: WILLOW Orientation & Client onboarding**

*RA: Please start by pretending you are talking with one of your patients. You have already completed the intake session and confirmed that the patient is a good fit for WILLOW.*

- A. *RA: Please provide me a brief, motivating orientation to WILLOW. Assume I am depressed and somewhat reluctant.*
  - Properly describes WILLOW as helping track outcomes**
  - Properly describes WILLOW as useful for guiding the delivery of an evidence based treatment**
  - Mentions why a tool like WILLOW is useful**
  - **Bonus Points: Deciding measures and when, make a plan with patient of what they would do and how the treatment will incorporate WILLOW features and tools**
- B. *RA: Explain to the client what they will have to do to get access to WILLOW after you create their account.*
  - Mentions email with account activation link**
  - Mentions that the email could be sent to junk mail**
  - -

**RA Prompt:** Can you be more specific? What parts of the process of activating the account is required in order to use WILLOW?

- *The account activation does not expire, but please prompt your patients to try and complete the activation process as soon as possible. The account activation process begins after your client clicks the link/button in the email and includes setting up 3 security questions, creating their password, and consenting to the Terms of Use for WILLOW. They must consent to the Terms of Use to be able to use WILLOW.*

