### Task 2: Patient Setup

RA: Please set up an account for a fictitious client, one with whom you have already had an intake session and whom you confirmed would be a good fit for the study and for using WILLOW.

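### Therapists who know their arm make an undefined fit judgment that, in the default flow, can end participation after consent and baseline, so removal could differ by arm

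*Protocol*

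**What the plan says.** Therapist Protocol, Step 7 (Orientation Call) reminds the therapist of the arm: "As you know, you have been randomly assigned to the" one condition or the other. It then describes a welcome or intake session to "introduce the study to them and gauge if they would be a good fit" and adds: "we ask that you use your clinical judgment during this session to assess if the client is appropriate for the study or not". Four exclusions follow: active mania or psychosis, alcohol or drug abuse or dependence, imminent suicide risk, and self-harm within 30 days. The instruction on removal is attached to these: "If you find your client meets any of the exclusion criteria, please let study staff know right away", and "We will work with you to discontinue the patient's participation in the study".

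Step 9 of the Therapist Protocol, under the First Session heading for both conditions, asks for a last check that the patient is eligible and appropriate, and lists the same four exclusions.

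Patient Protocol, Step 5 has staff ask the therapist after the session: "Is the client eligible / appropriate for the study"? Eligible patients go on to Step 6 (Scheduling Call). Ineligible patients have their participation discontinued.

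The Feature Review (Therapist Protocol, Step 8), taken only in the WILLOW arm, sets up Task 1 with "You have already completed the intake session and confirmed that the patient is a good fit for WILLOW" and Task 2 with a fictitious client "whom you confirmed would be a good fit for the study and for using WILLOW".

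The SAP's Analysis Strategy includes only patients who attended at least five sessions and does not mention patients removed at the welcome session.

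**The concern.** Randomisation is of therapists, so the therapist who judges fit already knows which treatment the patient would get. Fit and appropriateness are not defined beyond the four exclusions, and an unblinded therapist may read them in relation to the assigned treatment. The WILLOW training wording points towards that reading, and standard care has nothing comparable.

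If the two arms shed different kinds of patients after baseline, the groups analysed no longer differ only by treatment. More removal of poor-prognosis patients in the WILLOW arm would favour WILLOW; the opposite pattern would work against it. The plan would not reveal either. Patient Protocol Step 5 and Therapist Protocol Step 11 record eligibility status but not the criterion, and the five-session analysis set leaves out anyone removed at the welcome session.

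**Working it through.** The plan states no sample size, effect size or removal rate, so there is no figure to reproduce. The check is mainly a comparison of the text.

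**1. What standard applies, to whom, with what consequence**

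| Place | Arms | Standard | Stated consequence |
|---|---|---|---|
| Therapist Protocol Step 7 | both | fit; appropriate by clinical judgment; four exclusions | discontinuation, attached to the exclusions |
| Therapist Protocol Step 9, First Session | both | eligible and appropriate, then the same four exclusions | if ineligible, next steps are discussed and the study is told; if eligible, therapy continues |
| Patient Protocol Step 5 | both | eligible or appropriate | if ineligible, discontinued; only eligible patients go on to Step 6 |
| Therapist Protocol Step 8, Tasks 1 and 2 | WILLOW only | fit for the software | none; premise of an exercise |

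The first three rows disagree on whether appropriateness is a separate ground or shorthand for the four exclusions. Step 5 asks about both in one question and gives no path for a patient who is eligible but thought not appropriate.

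**2. Timing.** Under Patient Protocol Steps 3 and 4, the therapist or clinic is told that the patient is ready only after consent and baseline surveys. Step 5 then follows. Its opening note says that some clinics hold the session before the patient hears of the study, so the check precedes consent there.

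**3. Illustration of size (all inputs assumed).** Suppose one arm removes the fraction f with the worst perceived prognosis, and that perception correlates rho with the analysed outcome. For a normal outcome the retained mean shifts by

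shift = rho × φ(z_f) / (1 − f), in SD, where z_f is the f-quantile of the standard normal and φ its density.

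| f | φ(z_f)/(1−f) | rho = 0 | rho = 0.3 | rho = 0.5 |
|---|---|---|---|---|
| 5% | 0.109 | 0 | 0.033 | 0.054 |
| 10% | 0.195 | 0 | 0.058 | 0.097 |
| 20% | 0.350 | 0 | 0.105 | 0.175 |

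A simulation at f = 20%, rho = 0.5 gave 0.176.

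The bias is the difference between arms:

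- 10% against 10%: 0.
- 20% against 5%: 0.105 − 0.033 = 0.072 SD at rho = 0.3, and 0.175 − 0.054 = 0.121 SD at rho = 0.5.

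**4. Effect on false positives (assumed n per arm, clustering ignored).** With no true effect, SE = √(2/n) and the two-sided 5% test rejects with probability Φ(d/SE − 1.96) + Φ(−d/SE − 1.96), where d is the bias in SD.

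- n = 100, SE = 0.141: d = 0.10 gives 10.9%; d = 0.175 gives 23.6%.
- n = 50, SE = 0.2: d = 0.10 gives 7.9%; d = 0.175 gives 14.1%.

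**The case against.** The tempting stronger reading is that WILLOW therapists are trained to screen out patients unsuited to the software, which would be an arm-specific exclusion after baseline. The documents do not support it. The WILLOW wording is the premise of a role-play and of a set-up exercise with a fictitious client. No item in either task scores a judgment of fit. The review is described to the therapist as a test of familiarity with the software rather than of clinical skill, and pilot therapists skip it. The listed exclusions and the last check are the same in both arms, Step 7 attaches discontinuation to those exclusions, and no sentence orders removal for poor fit.

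Nor is the check always after consent. Besides the exception in Patient Protocol Step 5, Therapist Protocol Step 9 describes a welcome discussion before referral.

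Any figure for the bias rests on assumptions. One-arm removal is the extreme case, since both arms perform the check, and being unsuited to software need not mean a worse depression outcome.

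Finally, therapists choose whom to refer before consent (Therapist Protocol Steps 7 and 9). This is another route to selection, which tighter wording of the post-consent check does not close.

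All of this stands, and it limits the claim. It does not remove the inconsistency between Step 7's listed exclusions and the wider question in Patient Protocol Step 5. It also leaves an unblinded person answering that question, with no record of the ground.

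**Conclusion.** The point holds as a gap that leaves room for selection bias, not as a demonstrated bias. Therapists who know their arm make an open-ended judgment which, in the default flow, follows consent and baseline and can end participation. The texts disagree on how wide that judgment is, and the WILLOW-only exercises suggest a standard that standard care lacks. Removal that differs by arm is possible; nothing shows that it happened.

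The documents give no size. On the assumptions above the bias runs from zero (equal removal, or removal unrelated to outcome) to about 0.18 SD (20% removed in one arm only, rho = 0.5). A reader might want this as a share of the treatment effect, but the plan states no effect, so that ratio would only divide one assumption by another. The case for acting is that the correction is cheap.

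**What to change.** - Reconcile Patient Protocol Step 5 with Therapist Protocol Steps 7, 8 and 9. Post-consent removal from the study should rest on one written checklist, identical in both arms, made up of criteria the protocol already states: the four exclusions in Steps 7 and 9, and the Step 2 requirements that the patient be new to the clinic and not previously treated by that therapist. Decisions about the patient's care stay with the therapist and clinic.
- Drop the fit-for-WILLOW wording from Feature Review Tasks 1 and 2. The exercises work without it.
- Record the criterion for each removal and report removals by arm.
- Keep patients who meet no listed criterion in study follow-up even if their treatment changes or stops, as Step 7 already does for patients who leave therapy early.
- Add to the SAP an analysis of all consented eligible patients that does not apply the five-session rule, with stated assumptions for missing follow-up.

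The SAP is written in the past tense. If enrolment is over, what remains is the table of removals by arm, with whatever reasons can be recovered, and the added analysis.

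The cost is script wording, one log field, one table and one analysis. A few patients thought unsuited to the software would stay in the analysis. Selection by therapists before referral is not addressed.

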## Step 8: Feature Review (WILLOW Condition Only)

1. Send a reminder email to therapist the day before the scheduled feature review including the study guide *without* answers and join.me information
2. 15 minutes before call, log into the join.me meeting

### PROCEDURE:

Before starting the Pilot RCT, WILLOW therapists will receive individualized instruction and/or access to instructional tutorials from the EBPI research team in how to use WILLOW. WILLOW therapists will be required to demonstrate competencies in the following areas before beginning WILLOW use with a depressed patient. Competencies will be assessed during a virtual screen-share demonstration session that is expected to last approximately one hour. The test will be scheduled at the research therapist's convenience, and may be retaken as often as necessary until the participant is fully able to demonstrate competencies with all stated items. WILLOW therapists will be paid a \$100 Amazon gift card upon passing their competency test to compensate them for their time.

### INSTRUCTIONS:

<<SCRIPT>>: *Thank you for making this time today to demonstrate your ability to complete the various WILLOW tasks. As you know, we want to make sure you have had all the training and*

## WILLOW Full RCT Therapist Protocol

*support you need in order to use WILLOW thoroughly in treating your depressed patients. We have identified a number of essential tasks we call WILLOW Core Competencies that are necessary for you to use WILLOW well. In just a moment, I will ask you to perform a specific core competency. Because you will need to be able to use WILLOW efficiently with actual patients, I will be gauging your readiness based on your ability to correctly perform each task. Please keep in mind that I'm reviewing your familiarity and understanding of WILLOW, not your clinical skills. If you realize that you made a mistake in executing a task, you can repeat the task until you pass it before moving on to the next one. If you pass, terrific. If you don't, that is okay. I will just show you how to complete the task and we'll consider this as part of your training. Our goal is to make sure you are ready to go and have the training you need. We can redo this test as many times as needed until you pass with flying colors. Please do not have your study guide with answers open while we are going through the feature review.*

*Do you have any questions before we get started?*

### **Task 1: WILLOW Orientation & Client onboarding**

*RA: Please start by pretending you are talking with one of your patients. You have already completed the intake session and confirmed that the patient is a good fit for WILLOW.*

- A. *RA: Please provide me a brief, motivating orientation to WILLOW. Assume I am depressed and somewhat reluctant.*
  - Properly describes WILLOW as helping track outcomes**
  - Properly describes WILLOW as useful for guiding the delivery of an evidence based treatment**
  - Mentions why a tool like WILLOW is useful**
  - **Bonus Points: Deciding measures and when, make a plan with patient of what they would do and how the treatment will incorporate WILLOW features and tools**
- B. *RA: Explain to the client what they will have to do to get access to WILLOW after you create their account.*
  - Mentions email with account activation link**
  - Mentions that the email could be sent to junk mail**
  - -

**RA Prompt:** Can you be more specific? What parts of the process of activating the account is required in order to use WILLOW?

- *The account activation does not expire, but please prompt your patients to try and complete the activation process as soon as possible. The account activation process begins after your client clicks the link/button in the email and includes setting up 3 security questions, creating their password, and consenting to the Terms of Use for WILLOW. They must consent to the Terms of Use to be able to use WILLOW.*

## WILLOW Full RCT Therapist Protocol

C. RA: Explain the WILLOW patient portal to the client (what they do in WILLOW outside of session, what to expect to see).

- Mentions measures
- Mentions due dates
- Mentions homework
- Mentions homework progress reporting using the slide bar

RA Prompt: What would your client use their account for?

- Clients/patients would login between the sessions you have together
- WILLOW is accessible from any web accessible device (i.e., smart phone, tablet, laptop, desktop)
- If your client/patient hasn't completed their measures yet, a reminder email is sent out to them a day before the due date. BUT they do not need to wait for the email reminder, they can login to WILLOW at any time to do their homework and measures.

D. RA: Show me how you would find out where your patient is in the activation process.

- Goes to bottom of Patient Information page

E. RA: Imagine your client told you they never received the activation link. What would you do?

- Check junk mail
- Goes to bottom of Patient Information page and clicks Resend Account Activation Email

RA Prompt: Is there anything your client can do? Is there anything you would ask them to do first before you resend the activation link?

F. RA: Your client clicked the activation link but it showed an error message or the activation expired. What would you do?

- Click Resend Account Activation Email on patient information page

RA Prompt: This is a similar situation to the last question – your client is not able to start the activation process. What can you do from your therapist portal to restart the process for them?

### Task 2: Patient Setup

RA: Please set up an account for a fictitious client, one with whom you have already had an intake session and whom you confirmed would be a good fit for the study and for using WILLOW.

#### A. Patient Information

RA: For this you can use "[contact]" [replace xxx with today's date and write this into the chat so that the therapist may copy/paste into WILLOW]. Feel free to enter fake information into the other required fields

- Enters information for all required fields (email, nickname, DOB)

## WILLOW Full RCT Therapist Protocol

### B. Problems

RA: Assume this patient suffers from depression.

- Clicks checkbox for Depression**

### C. Protocol

RA: Please select Behavioral Activation as the protocol that you will use to treat this patient. And make sure to pair it with the problem you just indicated on the last page.

Click Save & Add Measures when you're done.

- Clicks checkbox for BA**
- Pairs with Depression**

### D. Measures

RA: Please select measures for this patient, including all the measures WILLOW recommends when treating depression with Behavioral Activation. Select another measure, not related to depression, and assign it on a 4-week basis.

Click Save & Add Measures when you're done.

- Selects BADS-SF, DASS-21, and PHQ-9S (recommended based on protocols)**
- Sets start dates**
- Selects another measure from Other Measures list**
- Sets frequency to 4 weeks**
- Sets start date for the other measure**

### E. Messages

RA: Assume that the patient would like to receive email reminders to complete measures. How would you do that?

- Checkmark to Send Reminder emails to patient**

### F. Treatment plan

RA: Now go to your treatment plan page. Please add diagnoses and goals.

Say you just remembered that your patient also indicated that they sometimes struggle with anger. You don't know if this is an actual problem yet, but you want to track it so you assign a measure. Go ahead and add a measure that assesses anger.

- Adds diagnosis/es**
- Adds goal(s)**
- Adds measure associated with sleep**
- Does these things from treatment plan page or the patient set up**

*You can add measures from the treatment plan page or you can go back to the measures page to add the measure. You can also add anger as a problem and then add the measure.*

### Task 3: Set up JITT sessions

## WILLOW Full RCT Therapist Protocol

A. *RA: Now we're going to set up your Behavioral Activation agendas from the treatment plan page. Can you show me how you would use the expert recommendation to assign a standard course of BA with this patient? Go ahead and customize the first two Agendas in your playlist by deleting a therapy task, reordering therapy tasks, and adding a new one from the list of Therapy Tasks on the left.*

- Adds the agendas from the Expert Suggested Playlist**
- Customizes the first 2 agendas**
  - delete a therapy task**
  - Rearrange therapy tasks**
  - Adds a therapy task**

B. *RA: Now let's say you realize that you only have 8 weeks to treat your patient, but the expert playlist is 10 weeks long. Show me how you would delete two agendas.*

- Deletes 2 agendas**

*To clarify deleting agendas for the BA protocol specifically, agendas 4 through 9 in the expert suggested playlist all contain the exact same therapy tasks. So in this scenario where you want to delete 2 agendas to accommodate for the shorter amount of time your patient has for therapy, you would NOT delete the agendas at the very end of the list. Instead you would delete agendas from the middle – between 4 and 9- so that you can still conduct the end of therapy agenda items.*

C. RA: Imagine that you are at session 9, but you decide with your client that it would be beneficial to do the tasks again for another session, show me how you would add an extra agenda before session 10.

- Adds another agenda**
- Does this by using Expert Suggested Playlist or by manually adding a new agenda**

*[Make sure therapist is aware of both ways to add a new agenda]*

D. *RA: Demonstrate how you would review the newly created Agendas so you can review the content, before having to use it with your patient. Please also demonstrate how you would review the content from an agenda that is 2 weeks in the future and also how you would review the content 5 minutes before a patient arrives.*

- Reviews therapy tasks of newly created agenda (from Treatment Plan or JITT Library)**
- Reviews therapy tasks of agenda 2 weeks in the future (from Treatment Plan or JITT Library)**
- Reviews therapy tasks 5 minutes before session (from Treatment Plan, Dashboard, or JITT Library)**

RA Prompt: Can you show me where else you can view the therapy content?

*[Make sure to tell the therapist all the places they can review the agenda content]*

E.

